6. From the beginning, being the initial contact of participant(s) through last contact with participant(s) please describe the task(s) they will be expected to perform. (How will you contact them? What will you have them do?) The proposed study addresses two specific aims with a multi-method, two-phase research project that will take place in South Dakota over a three-year period. The two phases are: (1) developing the wMammogram intervention (Aim 1) and (2) evaluating the feasibility and efficacy of the wMammogram (Aim 2). Phase 1 incorporates a Community Based Participatory Research (CBPR) approach and a series of focus groups with various stakeholders in AI communities to design a culturally informed and practically refined intervention. Phase 2 uses a randomized clinical trial (RCT) design with AI women. In phase one, after the approval of the Yankton Tribal Institutional Review Board (IRB), [name] will convene two focus groups ( $N=20$ ;  $n=10$  for each group). Each group will consist of AI community leaders/members and local health professionals with backgrounds in cancer and health management. The purpose of the two focus groups will be to obtain firsthand information about the general public/health care professionals' beliefs, attitudes, and values about breast cancer and screening, as well as barriers, motivators, and possible triggers for screening. In phase two, the wMammogram intervention will be implemented with AI women using the blinded RCT over a seven-day period. Assessments with a mixed methods approach will be conducted at three intervals: baseline, one-week post-intervention, six-month follow-up survey, and post-intervention focus group.
7. Have you attached letters of approval from any schools or businesses involved?
 

Yes       N/A

Section 2: Participants

8. Please state the maximum number of participants you plan on enrolling. **107**
9. Please describe the study populations by checking all that apply.
 

 Males	 Females	 University Students
 Non-English Speaking	 Students in Grades K-12	
10. Are you **specifically** targeting an ethnic group? Check any that apply.
 

 American Indian	 African American	 Caucasian

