IRB CODE NUMBER: 2019.053
NCT number: 05530603

University of South Dakota

Department of Social Work

**Intervention To Promote Breast Cancer Screening Among
American Indian Women**

Statistical Analysis

Date of Document: 09/24/2019

Statistical Analysis: Prior to our hypotheses tests, group equivalence in terms of baseline characteristics will be examined using t-tests and chi-square tests. For Hypothesis 1, investigators will compare the percentage of women from each condition who receive mammograms or have scheduled a mammography appointment using a chi-square test. Investigators will supplement this with logistic regression analyses to adjust for confounding covariates. For Hypothesis 2, the averages of score change (pre- to post-test) from the two conditions will be compared using the two-sample t-test, and/or the Wilcoxon rank-sum tests after assessing normality of the scores. The group difference in terms of changes in the given constructs will be tested by a mixed-effect analysis of variance (ANOVA). The mixed-effect ANOVA includes both within-subject (i.e., time: repeated measures) and between-subject factors (i.e., group: intervention versus control) and aims to examine whether there is an interaction between these two factors on the dependent variable. Bonferroni correction will be used to reduce the probability of Type 1 error for multiple comparisons. Investigators will supplement this with a regression analysis of score change in order to adjust for confounding covariates. For Hypothesis 3, averages of general satisfaction and effectiveness scores from each group will be compared using the two-sample t-test. Also, the percentage of participants from each group who endorse "yes" for the intention and recommendation items will be compared using the chi-square test. To minimize a potential non-participation bias, investigators will closely monitor and compare the first and fourth quartiles of responses for differences in background variables and key constructs. Investigators will also carefully document the response rate over the course of this project. IBM SPSS version 25 will be used for data analyses.

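### The Bonferroni correction in the Hypothesis 2 text is valid, but Holm's step-down procedure gives the same error control with equal or greater power

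*SAP*

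**What the plan says.** The SAP is a single Statistical Analysis paragraph covering three hypotheses.

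- **Hypothesis 1.** The investigators will "compare the percentage of women from each condition who receive mammograms or have scheduled a mammography appointment using a chi-square test", supplemented by logistic regression. No correction is mentioned here.
- **Hypothesis 2.** Change scores are compared by t-test and/or rank-sum test. Then "The group difference in terms of changes in the given constructs will be tested by a mixed-effect analysis of variance (ANOVA"), with the interaction of group and time as the target. The next sentence is the only one on multiplicity: "Bonferroni correction will be used to reduce the probability of Type 1 error for multiple comparisons". An adjusted regression of change scores follows.
- **Hypothesis 3.** Here "averages of general satisfaction and effectiveness scores from each group will be compared using the two-sample t-test", and the intention and recommendation items are compared by chi-square. No correction is mentioned here.

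The correction sentence names neither its family of tests nor a divisor. The number of Hypothesis 2 constructs is not given. Neither document states a significance level or sidedness, or calls any hypothesis primary. The protocol (IRB application, Section 2, question 8) caps enrolment at 107. It does not say whether that includes the 20 members of the Phase 1 focus groups.

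**The concern.** Bonferroni compares every p-value in a family of m tests with alpha/m. Holm orders the p-values and compares the smallest with alpha/m, the next with alpha/(m − 1), and so on, stopping at the first failure. Both hold the family-wise error rate at alpha, whatever the dependence between the tests. Every threshold in Holm's sequence is at least alpha/m, so Holm rejects everything that Bonferroni rejects and sometimes more.

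With at most 107 participants and several constructs to test, power per construct is likely to be limited. If the intervention moves several constructs together, single-step Bonferroni could leave some of those effects undeclared with no gain in error control.

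**Working it through.** The SAP gives no power, alpha or family-wise figure, so there is nothing of its own to reproduce.

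**Inputs**

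| Input | Value | Source |
|---|---|---|
| Maximum enrolment | 107 | Protocol, Section 2, question 8 |
| Arms | 53 and 54; alternatively 43 and 44 | Assumed 1:1 split of 107, or of 107 − 20 = 87 |
| Family | One group-by-time test per construct | Assumed |
| Number of constructs, m | 3, 4, 6 | Assumed |
| Level | Two-sided 0.05 | Assumed |
| Standardised difference in change | 0.5 per responding construct | Assumed |
| Correlation between test statistics | 0.4 | Assumed |

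**Step 1: thresholds.** For m = 4, Bonferroni uses 0.05/4 = 0.0125 throughout. Holm uses 0.05/4 = 0.0125, 0.05/3 = 0.0167, 0.05/2 = 0.025 and 0.05/1 = 0.05 in order.

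**Step 2: Bonferroni power in closed form.** The expected z-statistic is 0.5 × √(53 × 54/107) = 0.5 × √26.75 = 2.586. Power per construct is Φ(2.586 − critical value), ignoring the negligible opposite tail:

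- m = 3: critical value 2.394, Φ(0.192) = 0.58
- m = 4: critical value 2.498, Φ(0.088) = 0.54
- m = 6: critical value 2.638, Φ(−0.052) = 0.48

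**Step 3: Holm power by simulation, all constructs responding.** Based on 100,000 draws of equally correlated z-statistics with the mean above:

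| m | Bonferroni | Holm | Gain (points) |
|---|---|---|---|
| 3 | 0.577 | 0.656 | 7.9 |
| 4 | 0.535 | 0.624 | 8.9 |
| 6 | 0.478 | 0.575 | 9.7 |

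At 43 and 44 per arm the expected z is 0.5 × √(43 × 44/87) = 2.332. With m = 4, power goes from about 43% to about 51%.

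**Step 4: fewer constructs responding.** With m = 4 at 53 and 54, the gain per responding construct is about 0.1 points if one responds, 2 if two, 5 if three and 9 if all four. When only one construct responds, Holm can help only after it has already rejected a true null, which is rare.

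**Step 5: a larger effect.** With a standardised difference of 0.6, correlation 0 or 0.5, and 3 to 6 constructs all responding, average power rises from 0.67–0.76 to 0.78–0.84 at 53 per arm. At 43 per arm it rises from 0.56–0.65 to 0.66–0.74. Case by case the gain is about 7 to 13 points. If one construct responds, it is about 0.2 points or less.

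**Step 6: what does not change.** Both methods declare at least one construct significant exactly when the smallest p-value is at or below alpha/m. The chance of at least one rejection is therefore identical, and family-wise error stays at or below 0.05 under both.

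**The case against.** **Bonferroni is valid, so Holm is only a preference.** The first half stands: nothing in the SAP is wrong on this point. But the preference is not arbitrary, because Holm dominates Bonferroni without any further assumption.

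**The gain may be close to nothing.** This also stands. The 8 to 10 points apply when every construct responds, which is the case most favourable to Holm. If one construct responds the gain is about zero, and the documents do not say which case to expect.

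**The family may not be the constructs.** The correction sentence follows the repeated-measures ANOVA, and the protocol lists a baseline, a one-week and a six-month assessment. It could therefore mean contrasts between time points. If so, the power figures describe another family. Holm's dominance still holds for any family of two or more tests.

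**A reader might infer much more:** that Hypothesis 1 and four Hypothesis 3 tests each run uncorrected at 5%, so that the chance of a false claim of effectiveness is several times 5%. On that reading, with independent tests, the four Hypothesis 3 tests give 1 − 0.95⁴ = 18.5%, and adding Hypothesis 1 and a Hypothesis 2 family held at 5% gives 1 − 0.95⁶ = 26.5%. The documents do not support this as a finding:

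- No alpha is stated, so 5% per test is an assumption.
- That the correction excludes Hypotheses 1 and 3 is inferred from where the sentence stands. Its wording is not limited to Hypothesis 2.
- The count of four assumes one intention item and one recommendation item.
- Independence gives higher figures than positive correlation does. At correlation 0.7 the four-test figure is about 13%.
- Satisfaction and recommendation are acceptability outcomes. A false difference there is not a false claim that the intervention raises screening.

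Correcting the Hypothesis 3 tests is a trade-off, not a requirement. Even with each of the three hypotheses held at 5%, the any-error rate under independence would be 1 − 0.95³ = 14.3%.

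**Conclusion.** The point holds as an efficiency improvement, not as the correction of an error. For the Hypothesis 2 family, Holm gives the same family-wise control as the planned Bonferroni and never less power. Under the assumptions listed, average power per responding construct rises by about 0 points (one construct responds) to about 8 to 10 points (all of 3 to 6 respond) at 53 and 54 per arm. Of those inputs, only the maximum of 107 comes from the documents. The direction of the result does not depend on them; its size does.

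The unstated alpha, the undefined family and the absence of a named primary hypothesis are missing detail that should be filled in. They do not demonstrate an inflated error rate.

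**What to change.** Replace the Bonferroni sentence with wording such as: *For Hypothesis 2, the p-values of the group-by-time interaction tests for the constructs (list them) will be adjusted by Holm's step-down procedure to hold the family-wise error rate at two-sided 5%.* If the investigators meant another family, they should name that one; Holm applies equally.

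As accompanying clarification, state alpha and sidedness, name the primary hypothesis and label the others secondary. Hypothesis 1, the screening outcome, is the natural candidate, but the choice is the investigators', since the protocol pairs feasibility with efficacy. No correction of the Hypothesis 3 acceptability tests is asked for.

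The cost is a few sentences of SAP text and a hand calculation on the SPSS p-values. Simultaneous confidence intervals matching Holm are less simple than Bonferroni intervals, but the SAP mentions no confidence intervals. No extra participants or data are needed. The change should be made before the outcomes are compared between arms.
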